7.2.1.2 Treatment Period (Days 1 to 17)

All screening laboratory results and assessments must be available and all inclusion and exclusion criteria must have been satisfied prior to initiating treatment. The Treatment Period is from Day 1 until Day 17. For subjects in the SMT+PE-A 5% treatment group, PE-A 5% treatment may stop early depending on clinical response (see [Section 6.1.1](#), [Table 6-1](#), and

GRIFOLS Bioscience Industrial Group	Number	BIG-CL-PRT-000002	Version	6.0	Status	Retired	Effective Date	29-Mar-2023
	IG1407 - Effects of Plasma Exchange with Human Serum Albumin 5% (PE-A 5%) on Short-term Survival in Subjects with "Acute-On-Chronic Liver Failure" (ACLF) at High Risk of Hospital Mortality							60 of 102

[Table 6-2](#)). Subjects who remain in the hospital will continue to have Treatment Period assessments performed up through Hospital Discharge.

7.2.1.2.1 BASELINE/TREATMENT DAY 1

- Randomization (after confirmation of subject eligibility and prior to treatment)
- Record vital signs (SBP, DBP, HR, RR, T) (measured immediately prior to and immediately after the end of the PE-A 5% session in the SMT+PE-A 5% treatment group)
- Ascites assessment according to the ICA criteria ([Appendix 10](#))
- Record weight
- HE assessment ([Appendix 9](#))
- Hemodynamic assessment (MAP)
- Peripheral oxygen saturation (SpO₂) assessment
- Blood sample collection for (see [Table 7-1](#)):
 - Clinical laboratory assessments (eg, hematology, chemistry, coagulation) (measured immediately prior to and immediately after the end of the PE-A 5% session in the SMT+PE-A 5% treatment group)
 - Serum albumin concentration (measured immediately prior to and immediately after the end of the PE-A 5% session in the SMT+PE-A 5% treatment group)
 - Systemic inflammation assessment (CRP [in chemistry panel], WBC [in hematology panel], and procalcitonin)
 - Plasma biomarker retains for subjects in the SMT+PE-A 5% treatment group (plasma removed will be collected from the plasma bag after the first 15 minutes and the last 15 minutes of the PE-A 5% session)
- Record ACLF grade ([Table 2-1](#))
- Illness severity scoring: CLIF-C OF score, CLIF-C ACLF score, Child-Pugh score, and MELD score ([Appendix 4](#))
- PE-A 5% (SMT+PE-A 5% treatment group only)
- Record prior and concomitant medications
- Record AEs

7.2.1.2.2 TREATMENT DAYS 2, 4, 6, 8, 10, 12, 14, 16

- Record vital signs (SBP, DBP, HR, RR, T) measured immediately prior to and immediately after the end of the PE-A 5% session in the SMT+PE-A 5% treatment group
- Ascites assessment according to the ICA criteria ([Appendix 10](#))
- Record weight

GRIFOLS
 
Bioscience Industrial Group
	Number IG1407 - Effects of Plasma Exchange with Human Serum Albumin 5% (PE-A 5%) on Short-term Survival in Subjects with "Acute-On-Chronic Liver Failure" (ACLF) at High Risk of Hospital Mortality	BIG-CL-PRT-000002	Version 6.0	Status	Retired	Effective Date 29-Mar-2023	Page 61 of 102

- HE assessment ([Appendix 9](#))
- Hemodynamic assessment (MAP)
- Peripheral oxygen saturation (SpO₂) assessment
- Blood sample collection for (see [Table 7-1](#)):
 - Clinical laboratory assessments (eg, hematology, chemistry, coagulation) (measured immediately prior to and immediately after the end of the PE-A 5% session in the SMT+PE-A 5% treatment group)
 - Serum albumin concentration (measured immediately prior to and immediately after the end of the PE-A 5% session in the SMT+PE-A 5% treatment group)
 - Systemic inflammation assessment (CRP [in chemistry panel], WBC [in hematology panel], and procalcitonin)
 - Plasma biomarker retains for subjects in the SMT+PE-A 5% treatment group (plasma removed will be collected from the plasma bag after the first 15 minutes and the last 15 minutes of each PE-A 5% session)
- Record ACLF grade ([Table 2-1](#))
- Illness severity scoring: CLIF-C OF score, CLIF-C ACLF score, Child-Pugh score, and MELD score ([Appendix 4](#)).
- PE-A 5% (SMT+PE-A 5% treatment group only)
- Record prior and concomitant medications
- Record AEs

7.2.1.2.3 TREATMENT DAYS 3, 5, 7, 9, 11, 13, 15, 17

Record vital signs (SBP, DBP, HR, RR, T) on days when IVIG is administered, measured immediately prior to IVIG administration

- Ascites assessment according to the ICA criteria ([Appendix 10](#))
- Record weight
- HE assessment ([Appendix 9](#))
- Hemodynamic assessment (MAP)
- Peripheral oxygen saturation (SpO₂) assessment
- Infection surveillance if positive result obtained at Screening Visit using microbiology (cultures) including blood, urine, ascetic fluid, sputum, and pleural fluid. Day 3 sample will be collected if positive result at screening. Additional samples will be obtained upon clinical suspicion. All new infections will be recorded as AEs.
- Record ACLF grade ([Table 2-1](#))
- Illness severity scoring: CLIF-C OF score, CLIF-C ACLF score, Child-Pugh score, MELD score ([Appendix 4](#))

GRIFOLS
 
Bioscience Industrial Group
	Number	BIG-CL-PRT-000002	Version	6.0	Status	Retired	Effective Date	29-Mar-2023
	IG1407 - Effects of Plasma Exchange with Human Serum Albumin 5% (PE-A 5%) on Short-term Survival in Subjects with "Acute-On-Chronic Liver Failure" (ACLF) at High Risk of Hospital Mortality						Page	62 of 102

- IVIG 200 mg/kg infusion administered after every 2 PE-A 5% sessions (Days 3, 7, 11, or 15) (SMT+PE-A 5% treatment group only). See [Table 6-1](#) and [Table 6-2](#).
- IVIG 100 mg/kg infusion administered following the last, odd-numbered PE session on either days 9, 13, or 17 (SMT+PE-A 5% treatment group only). See [Table 6-1](#) and [Table 6-2](#).
- Blood biomarker retains for subjects in the SMT and SMT+PE-A 5% groups (Days 3, 7, and 17 only)
 - Blood sample will be collected before IVIG administration (SMT+PE-A 5% treatment group only)
- Record prior and concomitant medications
- Record AEs

7.2.1.3 Follow-Up Period

7.2.1.3.1 HOSPITAL DISCHARGE

- Record vital signs (SBP, DBP, HR, RR, T)
- Full physical examination (excluding breast and genitourinary examination)
- Ascites assessment according to the ICA criteria ([Appendix 10](#))
- HE assessment ([Appendix 9](#))
- Hemodynamic assessment (MAP)
- Peripheral oxygen saturation (SpO₂) assessment
- Blood sample collection for ([Table 7-1](#)):
 - Clinical laboratory assessments (eg, hematology, chemistry, coagulation)
 - Serum albumin concentration
 - Systemic inflammation assessment (CRP [in chemistry panel], WBC [in hematology panel], and procalcitonin)
 - Blood biomarker retains for subjects in the SMT and SMT+PE-A 5% groups
- Illness severity scoring: CLIF-C OF score, CLIF-C ACLF score, Child-Pugh score, and MELD score ([Appendix 4](#))
- Record ACLF grade ([Table 2-1](#))
- Record prior and concomitant medications
- Record AEs
- Record data on liver transplantation, subject survival, and cause of death

GRIFOLS Bioscience Industrial Group	Number	BIG-CL-PRT-000002	Version	6.0	Status	Retired	Effective Date	29-Mar-2023
	IG1407 - Effects of Plasma Exchange with Human Serum Albumin 5% (PE-A 5%) on Short-term Survival in Subjects with "Acute-On-Chronic Liver Failure" (ACLF) at High Risk of Hospital Mortality							63 of 102
							Page	

Subjects who remain in the hospital will continue to have treatment period assessments performed up through Hospital Discharge. Follow-up assessments for Days 21, 28, 60, and 90 will be performed for all subjects.

7.2.1.3.2 FOLLOW-UP VISITS (DAY 21 [+1 DAY], AND DAYS 28 [+ 2 DAYS], 60 [+ 2 DAYS], 90 [+ 2 DAYS])

- Record vital signs (SBP, DBP, HR, RR, T)
- Full physical examination (excluding breast and genitourinary examination)
- Ascites assessment according to the ICA criteria ([Appendix 10](#))
- HE assessment ([Appendix 9](#))
- Hemodynamic assessment (MAP)
- Peripheral oxygen saturation (SpO₂) assessment
- Blood sample collection for (see [Table 7-1](#)):
 - Clinical laboratory assessments (eg, hematology, chemistry, coagulation)
 - Serum albumin concentration
 - Systemic inflammation assessment (CRP [in chemistry panel], WBC [in hematology panel], and procalcitonin)
 - Blood biomarker retains (Days 28, 60, and 90) for subjects in the SMT and SMT+PE-A 5% groups
- Illness severity scoring: CLIF-C OF score, , CLIF-C ACLF score, Child-Pugh score, and MELD score([Appendix 4](#))
- Record ACLF grade ([Table 2-1](#))
- Record prior and concomitant medications
- Record AEs
- Record data on liver transplantation, subject survival, and cause of death on Days 28 and 90

7.2.1.3.3 FOLLOW-UP FOR EARLY DISCONTINUED SUBJECTS WITHDRAWN FROM THE STUDY

Subjects who discontinue from the study early should have all Day 90 procedures performed at the time of withdrawal (preferably within 1 week of withdrawal) including the following:

- Record vital signs (SBP, DBP, HR, RR, T)
- Full physical examination (excluding breast and genitourinary examination)
- Ascites assessment according to the ICA criteria ([Appendix 10](#))
- HE assessment ([Appendix 9](#))

- Hemodynamic assessment (MAP)
- Peripheral oxygen saturation (SpO₂) assessment
- Blood sample collection for (see [Table 7-1](#)):
 - Clinical laboratory assessments (eg, hematology, chemistry, coagulation)
 - Serum albumin concentration
 - Systemic inflammation assessment (CRP [in chemistry panel], WBC [in hematology panel], and procalcitonin)
 - Blood biomarker retains for subjects in the SMT and SMT+PE-A 5% groups
- Illness severity scoring: CLIF-C OF score, CLIF-C ACLF score, Child-Pugh score, and MELD score ([Appendix 4](#))
- Record ACLF grade ([Table 2-1](#))
- Record prior and concomitant medications
- Record AEs
- Record data on liver transplantation, subject survival, and cause of death

7.2.2 Description of Laboratory Tests and Procedures

Detailed descriptions of laboratory test procedures are located in the study Laboratory Manual. [Table 7-1](#) provides a summary of the laboratory tests conducted for this study.

Table 7-1 Name, Description, and Location of Laboratory Tests and Procedures

Test Panel	Description	Location
Hematology ^{a, b}	Hemoglobin, hematocrit, platelets, red blood cell count, white blood cell count with differential	Central
Chemistry ^{a, b}	Sodium, potassium, creatinine, blood urea nitrogen (BUN), calcium, magnesium, lactate dehydrogenase (LDH), aspartate Aminotransferase (AST), alanine Aminotransferase (ALT), gamma glutamyl transpeptidase (GGT), alkaline Phosphatase (ALP), glucose, total bilirubin, direct and indirect bilirubin, CRP, lactate, serum albumin	Central
Coagulation ^{a, b}	INR, fibrinogen, platelet count, prothrombin time	Central
Urine pregnancy test	Qualitative urine β-HCG will be performed at screening	Local
Systemic inflammation assessment	Procalcitonin, WBC (hematology panel), CRP (chemistry panel)	Central
Microbiology tests	CMV, PCR, and galactomannan antigen index	Central
Biomarker retains ^c	Blood biomarker	Central
	Post-PE-A 5% plasma biomarker obtained from plasma removed during the first 15 minutes and the last 15 minutes of the PE-A 5% session	

Abbreviations: ALP - alkaline phosphatase; ALT - alanine aminotransferase; AST - aspartate aminotransferase; BUN – blood urea nitrogen; CMV – cytomegalovirus; CRP – C-reactive protein; GGT – gamma-glutamyl transpeptidase; HCG - Human chorionic gonadotropin; INR – international normalized ratio; LDH – lactase dehydrogenase; PCR – polymerase chain reaction; WBC – white blood cells.

- ^a Laboratory tests required for determination of illness severity scores are presented in [Appendix 4](#). Local results used for illness severity scores will be entered into the eCRF and the subject's source documents.
- ^b To be collected before and after each PE session for the SMT+PE-A 5% treatment group.
- ^c Blood biomarker retains will be drawn for potential analysis of cytokines (interleukin [[IL]] 6 (IL-6), IL-8, IL-10, and tumor necrosis factor alpha found in the blood which are significantly correlated with disease activity. Blood samples and post-PE-A 5% plasma samples will be stored for possible future analysis of other biomarkers that may be identified throughout the length of the clinical study and beyond. This will help identify biomarkers during the critical period involved in the development and clinical course of ACLF in patients admitted to the study with AD of cirrhosis and dynamics of ACLF development which could impact future treatments and target the disease in its earliest stages. These samples will be frozen and retained for 15 years at which time if no analysis is performed, the samples will be destroyed. All clinical blood samples will need to be drawn first.

7.2.3 Drug Concentration Measurements

As indicated, serum albumin concentration (clinical chemistry laboratory assessment) will be sequentially measured during the clinical study and before and after each PE-A 5% session up to Day 90 visit.

8 ASSESSMENT OF SAFETY

8.1 Safety Variables

- The number of suspected ADRs, including adverse reactions (ARs), and incidence rate of subjects with suspected ADRs during the treatment period and within 72 hours after PE-A 5% completion (or after PE-A 5% stops) will be considered as the main safety variables. The number and incidence rate of overall AEs and SAEs, as well as deaths and discontinuations due to AEs will be also collected and analyzed.
- Vital signs will be recorded at each scheduled visit and in particular before and after each PE-A 5% session.
- Clinical laboratory test parameters (blood cell counts, platelet count, INR, fibrinogen, etc.) will also be assessed according to the study schedule.
- Physical examinations will be assessed according to the study schedule.
- According to the investigator's assessment, all clinically relevant changes in vital function and laboratory testing parameters findings will be considered AEs.

8.2 Methods and Timing for Assessing, Recording, and Analyzing Safety Parameters

For timing of safety assessments, please see [Section 7.2.1](#).

8.2.1 Adverse Events

Adverse events (includes suspected ADRs) occurring at any time between signing of the subject’s ICF and the last day of the subject’s participation (Day 90 visit or early discontinuation visit) in the clinical study will be reported and recorded on the appropriate subject’s eCRF entry and subject’s source documents.

It is the investigator’s responsibility to ensure that all AEs including suspected ADRs are appropriately recorded.

8.2.2 Vital Signs

Vital signs will be measured by a medically certified individual or a nurse according to his/her standard clinical practice.

The following vital signs will be assessed:

- Temperature
- Blood pressure (systolic and diastolic BP)
- Heart rate
- Respiratory rate

Vital signs will be routinely monitored by the study staff as detailed in [Appendix 1](#) and [Appendix 2](#). The investigator will be required to classify vital signs abnormalities as clinically significant or not according to his/her criteria. Results will be recorded in source documents and on the subject’s eCRF. Vital signs abnormalities judged by the investigator as clinically significant will be considered AEs.

8.2.3 Clinical Laboratory Evaluations

Considering the medical history and decompensated liver disease inherent in subjects with ACLF, certain laboratory abnormalities, while clinically significant, will be expected in this medical context, and would not indicate treatment-emergent worsening or a new AE (being instead an extension of medical history/underlying pre-existing conditions). Examples include: low platelet count, decreased albumin, prolonged prothrombin time/INR, elevated bilirubin, and abnormal transaminases. These conditions would be expected laboratory consequences of cirrhosis/decompensated liver diseases. These results would not be considered individual AEs as they most likely reflect manifestations of existing cirrhosis and hepatic decompensation, unless abnormalities worsen after initiation of study treatment and become accentuated to a medically significant degree in a treatment-emergent fashion.

Central clinical laboratory data for renal, hepatic, and hematological parameters will be listed for each clinical study subject.

The investigator will be required to classify laboratory results out of the normal range reported by the central laboratory as clinically significant or not according to his/her criteria.

GRIFOLS
 
Bioscience Industrial Group
	Number	BIG-CL-PRT-000002	Version	6.0	Status	Retired	Effective Date	29-Mar-2023
	IG1407 - Effects of Plasma Exchange with Human Serum Albumin 5% (PE-A 5%) on Short-term Survival in Subjects with "Acute-On-Chronic Liver Failure" (ACLF) at High Risk of Hospital Mortality						Page	67 of 102

Laboratory results out of the normal range judged by the investigator as clinically significant will be considered AEs.

8.2.4 Physical Examinations

A medically certified individual will conduct a physical examination.

8.3 Procedures for Eliciting Reports of and for Recording and Reporting Adverse Events and Intercurrent Illnesses

8.3.1 Warnings/Precautions

For complete information on Albutein 5% refer to the IB.

Plasma Exchange is a safe technique that may induce very well-known and therefore preventable and controllable AEs, according to the guidelines provided below. Considering the special vulnerability of the subjects studied, a number of precautions (in addition to the habitual measures) will be taken to minimize the risks of the procedure:

- PE will be carried out by specialized certified personnel, under direct and continuous supervision by the specialized physicians (intensivists, hepatologists, and hematologists).
- Vital signs and laboratory test parameters will be monitored more frequently than usual.

There are AEs that may be expected during the replacement procedure, due to the process of apheresis, the replacement fluid used, or as a result of the subject disease or idiosyncrasy. These AEs include, but not limited to, hypocalcaemia (manifesting as paresthesias, headache, vision alterations, nausea, cramps and chest oppression), anaemia and coagulation disorders secondary to coagulation factor dilution (mainly hypofibrinogenemia, with possible minor bleeding associated to severe thrombocytopenia), hypotension (accompanied by paleness, perspiration, bradycardia, nausea, vomiting, syncope, sphincter relaxation and seizures) (though the risk is minimal, since the infusion amount is equivalent to the extracted amount), allergic reactions with urticaria, dyspnea, wheezing, hypotension, tachycardia, facial reddening and palpebral edema, and AEs related to vascular access. Other events may be of psychological origin or may be inherent to the process, such as anxiety, headache, nausea, immunoglobulin level decreased, anemia, or pain after remaining immobile for several hours. However, these AEs will still be required to be reported.

8.3.2 Adverse Event Monitoring

Subjects must be carefully monitored for AEs. This monitoring includes clinical and laboratory tests and physical signs. Adverse events should be assessed in terms of their seriousness, severity, and causal relationship to the treatment.

Adverse events will be elicited by spontaneous reporting by the study individual or by a non-leading inquiry or direct observation by the study staff.

GRIFOLS
 
Bioscience Industrial Group
	Number IG1407 - Effects of Plasma Exchange with Human Serum Albumin 5% (PE-A 5%) on Short-term Survival in Subjects with "Acute-On-Chronic Liver Failure" (ACLF) at High Risk of Hospital Mortality	BIG-CL-PRT-000002	Version 6.0	Status	Retired	Effective Date	29-Mar-2023
						Page	68 of 102

8.3.3 Adverse Event Definitions

8.3.3.1 Adverse Events

An AE is defined as any untoward medical occurrence in a subject or clinical investigation subject administered a medicinal product or study treatment and which does not necessarily have a causal relationship with this administration. An AE can therefore be any unfavorable and unintended sign (including any abnormal laboratory finding, for example), symptom, or disease temporally associated with the use of a medicinal product, whether or not considered related to the medicinal product. This includes worsening of a pre-existing condition or increase in frequency of a pre-existing condition.

An AE is also defined as any occurrence that is new in onset, expected, or aggravated in severity or frequency from the baseline condition, or abnormal results or diagnostic procedures including laboratory test abnormalities.

In this clinical study, deterioration of the targeted disease and symptoms associated with the targeted disease will not be considered an AE as long as the deterioration is anticipated and there is no evidence suggesting a causal relationship between the study drug and the AE. Anticipated disease progression includes, but not limited to HE, gastrointestinal (GI) bleeding, portal hypertension, ascites, spontaneous bacterial peritonitis, HRS, and associated organ/system failure(s) (eg, liver, kidney, brain, coagulation, circulation, and/or lung) (see [Section 8.3.10](#)).

8.3.3.2 Suspected Adverse Drug Reactions/Adverse Reactions

All noxious and unintended responses to a medicinal product or study treatment related to any dose should be considered suspected ADRs. The phrase “responses to a medicinal product” means that a causal relationship between a medicinal product or study treatment and an AE is at least a reasonable possibility. An AR is a subset of the suspected ADRs that are deemed as definitely related to the treatment. See below for additional details.

8.3.4 Assessment of Causality of Adverse Event

The investigator is required to provide a causality assessment for each AE reported to the Sponsor. The Sponsor will consider the investigator’s causality assessment and also provide its own assessment. Causal relationship to the study drug will be established according to medical judgment on whether there is a **reasonable possibility of a causal relationship between the AE and the study drug**.

The investigator must determine and classify the AE causality according to the following categories:

Unrelated/Not related: there is not a reasonable possibility of causal relationship between the AE and the study drug.

Possibly related: there is evidence to suggest a causal relationship between the study drug and the AE.

Definitely related: there is a reason to conclude that the study drug caused the AE.

Criteria to assess the causal relationship should take into account of the following conditions:

- A plausible temporal sequence from the study drug administration to the AE onset
- Whether the event follows a known response pattern to the suspected treatment
- Whether the AE could be reasonably explained by the subject’s clinical state, comorbidities, or concomitant medications
- The occurrence of improvement on stopping/reducing the treatment (positive dechallenge) and/or reappearance of the event on repeated exposure (positive rechallenge)

For expedited safety reporting purposes, AEs assessed as either “definitely related” or “possibly related” will be considered POTENTIALLY RELATED or just RELATED.

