Investigational Product, Dose, and Mode of Administration:

Albutein® 5% is the investigational product.

PE-A 5% will be performed using 5% albumin (Albutein® 5%) as the main replacement fluid administered intravenously. One-point-two (1.2) plasma volumes will be exchanged per PE-A 5% session. Total blood volume (TBV) will be calculated according to Nadler's formula ([Appendix 3](#)). Plasma volume will be estimated from the calculated TBV and the

GRIFOLS Bioscience Industrial Group	Number	BIG-CL-PRT-000002	Version	6.0	Status	Retired	Effective Date	29-Mar-2023
	IG1407 - Effects of Plasma Exchange with Human Serum Albumin 5% (PE-A 5%) on Short-term Survival in Subjects with "Acute-On-Chronic Liver Failure" (ACLF) at High Risk of Hospital Mortality						Page	9 of 102

hematocrit (HCT). The volume to be exchanged will be considered as the volume to be infused (not the fluid to be removed).
 
The formula for calculating plasma volume to obtain the total volume to be exchanged is as follows:

$\text{Plasma volume} = \text{TBV} \times (1 - \text{HCT})$ $\text{Total volume to be exchanged} = \text{Plasma volume} \times 1.2$

Fresh frozen plasma (FFP) will be administered after the 5% albumin administration to prevent coagulopathy, and the PE-A 5% session is considered completed at the end of the FFP administration. A minimum of 4 and a maximum of 9 PE-A 5% sessions will be performed in subjects randomized to receive SMT+PE-A 5% (maximum treatment period: 17 days). The aim of the study is to achieve complete response (resolution of ACLF or improvement to ACLF-1a). The number of PE-A 5% sessions will be determined by the pattern of response to PE-A 5% treatment.
 
Intravenous immunoglobulins (IVIGs) will be administered at a dose of 200 mg/kg 1 day after every 2 PE-A 5% sessions in order to prevent the development of hypogammaglobulinemia and infection. In those subjects receiving an odd number of PE-A 5% sessions (eg, #5, #7, or #9 PE-A 5% sessions when they are the last PE session for the subject), IVIGs will be administered 1 day after this last PE-A 5% session at a dose of 100 mg/kg. Initial infusion rate of IVIGs will be 0.5 mL/kg/hour, increasing to a maximum rate of 2 mL/kg/hour if tolerance is adequate.

Duration of Treatment:
 
Subject participation (from screening to the final visit): Up to 100 days

Reference Therapy, Dose, and Mode of Administration:
 
Control Group: SMT per institution standards

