9.1.3.1 Adverse Events

Adverse events will be coded and classified using MedDRA® terms (system organ class and preferred terms).

When a causal relationship of an AE is classified by the investigator as definitely or possibly related, the event will be defined as a suspected ADR. A suspected ADR with a causal relationship of “definitely related” will be defined as an AR. The sponsor will consider the investigator’s causality assessment and also provide its own assessment. If there is any disagreement in causality assessment between the investigator and the sponsor, a separate summary of suspected ADRs/ARs will be provided.

For summary purpose, AEs will be classified as treatment-emergent AEs (TEAEs) or non-TEAEs depending on the comparison of AE onset date/time with the start date/time of study treatment. A TEAE will be defined as an AE which occurs between the start of study treatment and the final visit of the clinical study. A non-TEAE will be defined as an AE which occurs prior to the start of study treatment. Non-TEAEs and TEAEs will be summarized separately.

In addition, TEAEs, including suspected ADRs, will be summarized by each treatment group, system organ class, preferred term, causal-relationship, severity, and seriousness (serious versus non-serious) using descriptive statistics. At each level of summarization, a

subject will only be counted once per system organ class or preferred term using the most severe AE or the AE with the strongest causal relationship to the treatment.

AEs (including suspected ADRs) temporally associated with PE-A 5% (ie, those occurring during a PE session or within 72 hours after the completion of a PE session) will be summarized by presenting incidences and percentages and listed.

Subjects with SAEs, AEs leading to death, or who withdraw from the study because of an AE will also be individually listed and summarized.

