10.1 Adverse Events

Adverse Events are coded using the MedDRA coding dictionary (a version within 1 year of the data base lock).

A treatment emergent adverse event (TEAE) is defined in section [6.1.6](#). Non-TEAEs and TEAEs will be summarized separately.

A suspected adverse drug reaction (ADR) is an adverse event with causal relationship of “definitely related” or “possibly related”, as classified by the investigator. An adverse reaction (AR) is an adverse event with causal relationship of “definitely related”, as classified by the investigator.

An temporally associated AE is an AE that is temporally associated with PE-A 5% and is identified as an AE that occurs during a PE session, or within 72 hours following after the completion of a PE session. These definitions only apply to subjects in the SMT+PE-A 5% group.

All adverse events, both treatment-emergent and non-treatment emergent, will be included in a listing, with a flag to distinguish whether the event is treatment-emergent.

An overall summary of TEAEs will present the number of TEAEs, and the number and percentage of subjects with TEAEs, in the following categories:

- Non-TEAE (AE with Onset Prior to Treatment)
- TEAE
- Suspected ADR
- AR
- TEAE Leading to Death
- Serious TEAE
- Serious Suspected ADR
- Non- Serious Suspected ADR
- Serious AR
- Non-Serious AR
- Non-Serious TEAE
- TEAE Leading to Drug Interruption
- TEAE Leading to Drug Withdrawal
- TEAE Leading to Study Withdrawal
- Temporally Associated TEAEs

In addition, TEAEs will be summarized in the following ways:

- SOC / PT – summary of number of TEAEs and number/percentage of subjects with at least one TEAE by treatment, SOC, and preferred term
 - A select subset of TEAE summaries will also include number of events by SOC and preferred term
- SOC/PT/Severity – summary of number of TEAEs and number/percentage of subjects with at least one TEAE by treatment, SOC, preferred term, and severity

Instituto Grifols, S.A. / Protocol IG1407

- SOC / PT / Causality – summary of number of TEAEs and number/percentage of subjects with at least one TEAE by treatment, SOC, preferred term, and causality

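### Causality is rated against an undefined study drug while suspected ADRs are defined by study treatment, so reactions to other parts of PE-A 5% can be left out of the ADR counts; SAP 10.1 also omits the sponsor-disagreement summary

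*Protocol*

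**What the plan says.** Protocol 8.3.3.2 sets a wide definition: "All noxious and unintended responses to a medicinal product or study treatment related to any dose should be considered suspected ADRs". Protocol 8.3.4 then gives the three categories that investigators have to use, and each is worded against the study drug. The lowest category is "Unrelated/Not related: there is not a reasonable possibility of causal relationship between the AE and the study drug". The middle one is worded as "Possibly related: there is evidence to suggest a causal relationship between the study drug and the AE". For the highest, the text is "Definitely related: there is a reason to conclude that the study drug caused the AE". The protocol does not define study drug. Its synopsis states "Albutein® 5% is the investigational product", and Section 4.4.1.2 names the same product.

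On known harms, Protocol 8.3.1 says: "There are AEs that may be expected during the replacement procedure, due to the process of apheresis, the replacement fluid used". It goes on to list vascular access events, and it requires all of these to be reported.

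On counting, Protocol 9.1.3.1 turns an investigator rating of possibly or definitely related into a suspected ADR, and definitely related into an AR. It adds: "If there is any disagreement in causality assessment between the investigator and the sponsor, a separate summary of suspected ADRs/ARs will be provided". SAP 10.1 uses causality "as classified by the investigator" and plans no table based on the sponsor's assessment.

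**The concern.** The safety objective is the profile of PE-A 5%. That treatment is an apheresis procedure with vascular access, citrate or heparin, Albutein and FFP, accompanied by protocol-mandated IVIG. The definition of a suspected ADR is wide enough to cover it, but the scale that produces the data may not be.

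If a site takes study drug to mean Albutein, a reaction it attributes wholly to another component is properly rated not related and never reaches the suspected-ADR or AR tables. Protocol 8.1 makes suspected ADRs the main safety variables, and SAP 5.4.2 lists suspected ADRs and ARs among them. The incidence could then reflect how sites read one undefined term as well as how often the treatment harms patients.

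**Working it through.** No published figure needs reproducing. The check follows an event from rating to table.

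1. **Rated object.** In 8.3.4 the governing sentence and all three categories refer to the study drug. The surrounding text is wider. Section 8.3.2 asks for causal relationship to the treatment, 8.3.8 for relationship to treatment, and two of the criteria in 8.3.4 speak of the treatment. The documents therefore support two readings.

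2. **Capture.** The AE eCRF (Protocol 8.3.8) has one three-level causality field. It has no separate rating for procedure, access, anticoagulant, FFP or IVIG, so the object of a given rating cannot be recovered from that field.

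3. **Components under each reading.**
   - Albutein 5% is covered either way.
   - FFP is covered if study drug means the exchange, because the session ends only when FFP has been given (Protocol 6.1.1.1). It is not covered if study drug means Albutein, and SAP 8.2 tabulates it as a blood product.
   - Procedure, access and citrate or heparin are covered only on the wide reading.
   - IVIG is the least secure. It is given a day after a session, is recorded under concomitant therapy (Protocol 6.2) and is tabulated with concomitant medications (SAP 8.1). One criterion in 8.3.4 asks whether concomitant medication could explain the event. Even a site that equates study drug with the exchange session could rate an IVIG reaction not related.

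4. **Effect on the count.** Let *a* be the proportion of PE-arm subjects with a reaction for which Albutein is a reasonable possibility. Let *c* be the proportion whose only reactions are to other components, and *s* the share of that second group rated on the narrow reading. Reported suspected-ADR incidence is then *a* + (1 − *s*)*c*. It equals *a* + *c* when *s* = 0 and *a* when *s* = 1. The documents give no value for *a*, *c* or *s*, so the shortfall *sc* is bounded by 0 and *c* but cannot be estimated.

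5. **Progression exemption.** Sections 8.3.3.1 and 8.3.10 exempt anticipated deterioration, including GI bleeding and coagulation failure, from being an AE unless there is evidence linking it to the study drug. On the narrow reading, bleeding linked to the procedure or anticoagulant could be filed as progression and would then miss every AE table. It would still appear by arm under SAP 10.2 as a disease-related complication.

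6. **What the temporally associated table covers.** It takes AEs during a session or within 72 hours after one, whatever the causality. Sessions fall on Days 1, 2, 4, 6 and so on, at most 48 hours apart. If the schedule is kept, the windows join up from the first session to 72 hours after the last: to about Day 9 after four sessions (6 + 3) and Day 19 after nine (16 + 3). IVIG a day after the last session still leaves about 72 − 24 = 48 hours. The table therefore catches acute reactions to any component. It misses later ones and anything filed as progression, and it exists for the PE arm only.

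7. **Sponsor summary.** SAP 10.1's table grid has no row for sponsor causality, and SAP Section 12 does not list the omission although it does declare added TEAE categories. This gap exists on either reading of study drug.

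**The case against.** The best defence is that the protocol, read as a whole, asks for causality against the treatment. Sections 8.3.2, 8.3.3.2 and 8.3.8 say so, 8.3.3.2 points forward to 8.3.4 for detail, and SAP 6.1.4 and 8.4 attach study drug to the exchange. That stands as evidence that the narrow reading is not the only one. It does not settle the matter, because the categories themselves are worded otherwise and investigators rated under the protocol.

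Several stronger conclusions are tempting and are not supported:

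- **That the protocol equates study drug with Albutein.** This is an inference from the single named product.
- **That all the harms listed in 8.3.1 would be rated not related.** That rating requires no reasonable possibility of a causal link. Albumin is the main replacement fluid, and dilutional coagulation disorders and allergic reactions can plausibly involve it. Access and IVIG events are the clearer cases.
- **That the harms disappear from safety reporting.** Those recorded as AEs stay in the TEAE and serious TEAE tables by arm and in the temporally associated table. SAP 5.4.2 also lists overall AEs, SAEs, deaths and discontinuations among the main safety variables.
- **That the sponsor summary would have corrected the problem.** It is conditional on disagreement, and the sponsor's assessment falls under the same 8.3.4 wording. It is at most a partial safeguard.

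**Conclusion.** The concern holds as an internal inconsistency with a possible effect on one group of main safety outputs. Definition and rating scale use different objects, one of them undefined, and only the scale feeds the suspected-ADR and AR counts. Those counts can understate reactions to the procedure, access, anticoagulant, IVIG and, on the narrow reading, FFP, and they can vary by site. A reader might infer that they will understate harm. The documents show only that the wording permits it, by an amount between zero and the full share of subjects whose only reactions are to other components.

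This rests on two assumptions: that at least some sites took the narrow reading, and that some reactions were attributed wholly to a component other than Albutein. The missing sponsor-disagreement summary is a separate, undeclared departure from Protocol 9.1.3.1 and depends on neither. Causality-independent tables limit the damage, so the point concerns how the ADR results are defined and presented. The primary efficacy analysis is not affected.

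**What to change.** **Protocol.** Sections 8.3.3.1, 8.3.3.2, 8.3.4 and 8.3.10 should be reconciled on one defined term covering the whole PE-A 5% treatment: procedure and access, Albutein 5%, FFP, anticoagulant and IVIG. The last patient visit was 14 April 2025 (SAP Section 2), so this cannot change ratings already made. It matters for the record and for any further use of the template.

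**SAP 10.1.** This is where results can still be affected.

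- Restore the Protocol 9.1.3.1 summary of suspected ADRs and ARs where sponsor and investigator disagree, or declare and justify its removal in Section 12.
- State which object the collected causality ratings refer to and, if site practice varied, say so in the clinical study report.
- Place the planned temporally associated TEAE table beside the suspected-ADR table as the causality-independent measure for the PE arm, noting its 72-hour limit and the absence of a control-arm counterpart.

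**Cost.** One added summary, using an assessment that 8.3.4 already requires of the sponsor, plus a short statement and a change of table order. If causality is to be re-rated against the whole treatment, the sponsor has to re-review events, which is real extra work and should be labelled as retrospective. No dose, schedule or stopping rule is touched.
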